### 10.A.1. Aim 1 Other Analyses

We plan to explore whether treatment effects differ among patient groups defined by age, race/ethnicity, socioeconomic status, and comorbidity. While we anticipate that on average across all patient groups telehealth care will reduce SBP by 5 mm Hg more than clinic-based care, we will separately quantify the treatment effect for all H1 outcomes among targeted patient subgroups. The H1 analytic models can be easily adapted to include parameters for patient covariates as well as interactions of patient covariates with time or time by treatment.

[figure not shown]
The H1 analytic models can be readily adapted for secondary and sensitivity analyses. As presented, H1.1 assumes a linear rate of change in SBP over time. The model can be readily adapted to assess the immediate effectiveness of telehealth during the first 6 months following eligibility separately from the 6- to 12- and 12- to 24-month periods, when short-term improvements in SBP or PROs may be differentially maintained over a longer time frame. Similarly, parameters  $\gamma_{01}$  and  $\gamma_{11}$  can be allowed to vary randomly so that the rate of SBP change is different for each of the 20 randomized clinics. We could then assess, for example, whether clinic-specific rates of change are related to clinic characteristics or the fidelity with which the care model was implemented.

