## **2. Objectives**

### **2.A. Aim 1**

In a pragmatic cluster-randomized trial in patients with uncontrolled hypertension, compare the effects of two evidence-based strategies on lowering blood pressure and other outcomes important to patients: best-practice clinic-based care and home-based telehealth care.

**Hypothesis 1.1:** Compared with patients in clinics assigned to clinic-based care, patients in clinics assigned to telehealth care will have a 5 mm Hg greater change in systolic blood pressure over 12 months of follow up.

**Hypothesis 1.2:** Compared with patients in clinics assigned to clinic-based care, patients in clinics assigned to telehealth care will report: a) fewer treatment side effects; b) better ratings of patient experience of hypertension care; and c) higher self-monitoring rates and confidence in self-care.

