Suggestions from the focus groups and analyses of study data were used to modify our previous telehealth care intervention in the following ways. **1)** The qualifications of pharmacists to treat hypertension and the collaborative nature of their work with the patient's PCP will be emphasized. **2)** In order to remove barriers for team care, home BP data will be transmitted and stored in the HealthPartners Epic EHR, rather than in a password-protected third-party Web site. Home BP data will be maintained in a flowsheet that is separate from BP measured during clinic visits. **3)** Trajectories of BP during the Hyperlink study showed maximum BP lowering after an average of about 3 months, with little additional BP lowering during the remainder of the 6 months of intensive intervention and 6 additional months of maintenance. Therefore, rather than having a fixed duration, the telehealth care intervention will be flexible and tailored to individual patients' needs. **4)** Patients will have several options for transmitting home BP data (further details below). In any case, patients will be given their own BP monitor for long-term use.

Telehealth care clinics will offer best-practice clinic-based care, but eligible patients in these clinics will be referred for telehealth care with systematic home BP telemonitoring and BP management through the MTM pharmacist. Referrals will take place using the same hypertension follow up orders used for clinic-based care, but the default will be MTM pharmacist follow-up. There is currently a high rate of appointment completion following referral to MTM pharmacists. As in the clinic-based care group, the study will foster reliable processes to improve the consistency with which the order set is used and uncontrolled BP is re-assessed by an MTM pharmacist within 4 weeks. Following an initial face-to-face intake visit, the MTM pharmacist and patient will communicate by telephone or secure e-mail (according to patient preference) at regular intervals, adjusting medication using established care protocols and collaborative practice agreements until BP control has been achieved. Pharmacists will also support lifestyle changes and adherence to treatment. Other CV risk factors including smoking, hyperlipidemia, hyperglycemia in diabetic patients, and use of aspirin will be addressed as needed using evidence-based protocols, since this is the customary practice of MTM pharmacists at HealthPartners.

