### **7.A. Primary Aim 1 outcome**

The primary outcome is change in SBP after 12 months of follow-up (H1.1). SBP values that are routinely collected in primary care will be extracted from the vital signs field in the EHR at the two qualifying encounters and at all subsequent qualifying encounters over the next 24 months for all enrolled patients.

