## **10. Analysis**

## 10.A Aim 1 Primary and Secondary Analyses

The Aim 1 hypotheses pertain to the effectiveness of telehealth care, predicting that, relative to clinic-based care, it will improve SBP by a practically meaningful 5 mm Hg after 12 months of follow up (H1.1) and patient-reported outcomes (PRO) after 6 months of follow up (H1.2). H1.1 will be tested using random coefficients models in which post-enrollment SBP values will be predicted from clinic-randomized treatment group (Telehealth), time elapsed from enrollment to the SBP (YEARS), and the treatment by time interaction. The most basic form of the H1.1 model will be:

$$SBP_{ij} = \gamma_{00} + \gamma_{10} \text{Telehealth}_i + \gamma_{01} \text{YEARS}_j + \gamma_{11} \text{Telehealth}_i * \text{YEARS}_j + [u_{i0} + e_{ij}],$$

where EHR-derived SBP values documented at all qualifying encounters for 24 months will vary randomly across randomized clinics ( $u_{i0}$ ) and time ( $e_{ij}$ ). Enrolled patients will be assigned to the treatment group to which their clinic is randomly assigned, regardless of their adherence to any component of the clinic-based care or telehealth care approaches. YEARS will be scaled so that 0 represents the date of the primary care encounter at which the patient was enrolled in the study and 1 represents 365 days later. Parameter  $\gamma_{01}$  will therefore estimate the annual rate of change in SBP among clinic-based care patients, and parameter  $\gamma_{11}$  will estimate the difference in rate of SBP change among telehealth relative to clinic-based care patients. The H1.1 model will be adapted for H1.2 by replacing the YEARS component of  $\gamma_{01}$  and  $\gamma_{11}$  with a dummy indicator (6M) for whether the PRO is an enrollment or 6-month survey response.

SBP and PRO are expected to be approximately normally distributed, although the suitability of alternate error distributions and link functions will be assessed if their distributions depart from expectations. Should we observe an imbalance between study groups in the characteristics of randomized clinics, particularly in factors that moderate the fidelity with which the care models may be implemented, we may include clinic-level variables (e.g., % patients >65) as covariates or treatment modifiers, as appropriate.

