SBP values are expected to decline over time among clinic-based care patients so that  $\gamma_{01} < 0$ . H1.1 will be most strongly supported if  $\gamma_{11} \leq -5.0$  and  $P < .05$ , so that the estimated rate at which SBP values improved over 12 months was at least 5 mm Hg greater among telehealth patients relative to clinic-based patients. PROs are expected to be similar at baseline but months to have improved among telehealth patients by 6 months so that  $\gamma_{11} > 0$  and  $P < .05$ .

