### 4. Patient outcomes and safety monitoring

4.1 Effectiveness, clinical outcomes. The primary clinical effectiveness analyses will quantify the extent to which there is a larger reduction, or less of an increase, in systolic blood pressure in the 12 months following Hyperlink enrollment among patients in telehealth relative to clinic-based care clinics. Secondary analyses will address whether similar changes are observed in clinical outcomes such as diastolic blood pressure, lipid levels and cardiovascular risk; whether antihypertensive or lipid medications are more aggressively managed among telehealth patients; and whether telehealth patients are less likely to be current smokers. Table 1 summarizes all primary and secondary outcomes. For each clinical outcome, we plan to include all available data in the 24 months following enrollment in the analyses. However, effectiveness will be assessed via a comparison of the rate of change in the first 12 months post-enrollment.

All clinical outcomes data will be documented in the electronic health record or the Hyperlink data repository as observations accrue. Their immediate availability will make it feasible to check assumptions of the clinical effectiveness analyses such as balance on key covariates prior to intervention exposure; the central tendency, variance and distribution of clinical outcomes; the number and timing of observations per person; the viability of assuming a linear rate of change in outcomes, and how non-linear trends might be addressed; and the magnitude of the design effects introduced by cluster randomization and repeated measures within patients. These assumptions can be investigated in aggregate as data accrue, and by treatment group or clinic at the DSMB's request, to inform the conduct of the primary effectiveness analyses.

4.2 Effectiveness, patient outcomes. The effectiveness of the clinic-based care and telehealth care interventions at improving patient reports of side effects, satisfaction with care and confidence in self-care will be assessed by comparing

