enrolled n	cumulative, monthly; aggregate and by treatment, clinic a	open
patient demographics	enrollment status, treatment, clinic a	open
clinical measures at enrollment	enrollment status, treatment, clinic a	open
Fidelity		
infrastructure and policies	monthly by treatment	open
hypertension care processes	monthly by treatment	open
telehealth care processes	monthly within telehealth	open
Clinical outcomes, post-enrollment		
patient covariates (enrollment)	aggregate, treatment b	open
outcome counts	aggregate	open
	treatment	closed
outcome variance	aggregate	open
outcome descriptives	aggregate	open
	treatment by month	closed
Patient reported outcomes, post-enrollment		
outcome counts	aggregate	open

	treatment, missing mechanisms	closed
outcome descriptives	aggregate	open
	treatment by time	closed
Safety outcomes		
diagnoses	aggregate by time, treatment by time, as treated by time b	open
lab measures	aggregate by time, treatment by time, as treated by time b	open
Primary analyses		
H1.1 12m clinical effectiveness	treatment by time trend interaction enrollment to 12m	open
H1.2 PRO change	treatment by time interaction, B-6m	open
H1.1 effectiveness full model	treatment by time trend interaction enrollment to 24m	open
Aim 2 PRO maintenance	12m, 24m descriptives	open
a Clinics will be identified by number rather than name.		
b Treatment groups will be identified by random labels rather than “clinic-based” or “telehealth”		

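### The primary test is a 24-month straight-line slope, which does not estimate the stated 12-month difference in SBP if the effect arrives early and then holds

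*Combined protocol and SAP*

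**What the plan says.** Hypothesis 1.1 (section 2.A) predicts for telehealth a "5 mm Hg greater change in systolic blood pressure over 12 months of follow up", and section 7.A makes SBP change at 12 months the primary outcome.

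The H1.1 model in section 10.A is fitted to "EHR-derived SBP values documented at all qualifying encounters for 24 months". It has a treatment term (γ10), a linear term in years (γ01) and their product (γ11). H1.1 is most strongly supported if the test is significant at .05 and γ11 is −5.0 or lower, which the plan explains as "so that the estimated rate at which SBP values improved over 12 months was at least 5 mm Hg greater among telehealth patients". Section 10.A.1 adds: "As presented, H1.1 assumes a linear rate of change in SBP over time". It mentions separate 0–6, 6–12 and 12–24 month periods as an adaptation for secondary and sensitivity work.

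On the expected shape, section 5.B says: "Trajectories of BP during the Hyperlink study showed maximum BP lowering after an average of about 3 months", with little further change over the remaining intervention period. Section 1.B.2.2 reports that the previous trial's benefit was sustained at 12 and 18 months. Section 5.B.2 expects most patients to need 3 or 4 months of telehealth management.

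The Data and Safety Monitoring Plan (section 15) reads differently. Its 4.1 says: "However, effectiveness will be assessed via a comparison of the rate of change in the first 12 months post-enrollment". Its 4.5 schedules that comparison for 2020 and distinguishes it from the full H1.1 model, which follows in 2021. Table 4 lists both, the later one as "treatment by time trend interaction enrollment to 24m".

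**The concern.** A slope over 24 months equals a 12-month difference only if the arms start level and keep diverging at a constant rate. On that reading, γ11 = −5 implies a difference of −10 mm Hg at 24 months, which the plan nowhere predicts. Its own evidence points to early separation followed by a plateau. With that shape, part of the early separation is absorbed by γ10, and the flat later stretch pulls γ11 toward zero.

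At stake are the size of the primary estimate and the power claimed for it. The estimate would also depend on when routine visits happen, which the trial does not control, and on whether the enrollment SBP is an outcome row. Section 10.A speaks of readings after enrollment; section 7.A also extracts SBP at the qualifying encounters.

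**Working it through.** **1. Reproduce the plan's power figure.** Inputs from section 10.A.3: 20 clinics × 100 patients = 2000, 3 SBP values each over 24 months, clinic ICC .01 to .03, SD 20.4, 80% power, two-sided .05. The standardized detectable slope difference is

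(1.960 + 0.842) × √[4(1 − ICC)(1 + 99·ICC) / (2000·Sxx)].

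With readings at years 0, 1 and 2, Sxx = 1 + 0 + 1 = 2.

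- ICC .01: 2.802 × √(4 × .99 × 1.99 / 4000) = .124
- ICC .03: 2.802 × √(4 × .97 × 3.97 / 4000) = .174

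Both match the plan. The spacing is inferred from this fit; the plan does not state it. The plan's 2.53 and 3.55 mm Hg imply standard errors of 2.53/2.80 = 0.90 and 3.55/2.80 = 1.27.

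**2. Put a sustained −5 through the same layout.** Assume that the arms are equal at enrollment and that the difference D falls linearly to −5 at 3 months and stays there. At years 0, 1 and 2, D = 0, −5, −5, and the fitted slope is

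[(−1)(0) + (0)(−5) + (1)(−5)] / 2 = −2.5 mm Hg per year.

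In this layout the slope is half of (D at year 2 minus D at year 0), so the 3-month ramp is not needed: any −5 still present at year 2 gives −2.5.

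**3. Vary visit timing, window and the enrollment row.** The table gives the least-squares slope of D on time, with a free intercept. All visit patterns are assumptions.

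| Window | Readings | Enrollment SBP a row? | γ11 |
|---|---|---|---|
| 24 months | years 0, 1, 2 | yes | −2.50 |
| 24 months | every 6 months | yes | −2.00 |
| 24 months | every 3 months | yes | −1.33 |
| 24 months | concentrated early* | yes | −3.2 to −4.1 |
| 24 months | uniform | no | −0.86 |
| 24 months | concentrated early* | no | −2.3 |
| 24 months | all at month 3 or later | no | 0.00 |
| 12 months | 0, 6, 12 months | yes | −5.00 |
| 12 months | every 3 months | yes | −4.00 |
| 12 months | monthly | yes | −3.52 |
| 12 months | irregular | yes | −4.8 to −6.7 |
| 12 months | uniform | no | −3.1 |
| 12 months | every 3 months from month 3 | no | 0.00 |
| 12 months | irregular, early | no | −4.1 to −5.0 |

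*Two, three or six visits per patient with exponential times, mean 6 months; draws beyond 24 months are replaced by uniform ones.

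Worked example, uniform over 24 months: cov(t, D) = −0.2865 and var(t) = 0.3333, so the slope is −0.86. The fitted intercept is about −3.83, so the same line implies about −4.69 at year 1. Most of the effect sits in γ10, which is not tested. Refitting the irregular schedules with the plan's patient ICC of .28 moved the slopes by less than 0.2.

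**4. Power at the plan's own standard errors.** Power = Φ(|γ11|/SE − 1.96).

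- γ11 = −5: above 99% (SE 0.90) and 98% (SE 1.27)
- γ11 = −2.5: Φ(2.77 − 1.96) = 79% and Φ(1.97 − 1.96) = 51%

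**The case against.** The strongest reply is that the monitoring plan assesses effectiveness over the first 12 months, where a linear slope can come close to −5. That is true, and it limits the point. But it holds only if the enrollment SBP is a row; without it the 12-month slope runs from 0 to about −5. Section 15, 4.5 also says that this comparison is not the full H1.1 model, and no passage states which one is confirmatory.

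Second, the plan recognises non-linearity. Section 10.A calls the equation its most basic form, and section 15, 4.1 says that linearity, and ways of handling its failure, can be examined as data accrue to inform the primary analysis. That stands as awareness, but no remedy is fixed in advance for the primary test.

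Third, the plateau is inferred. It comes from BP trajectories in a trial against usual care, whereas the comparator here is best-practice care with early follow-up. This also stands: the shape is an assumption.

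Fourth, the standard errors carry the full clinic inflation 1 + 99·ICC. With a random clinic intercept and no random clinic slopes, that intercept largely cancels from a slope. The standard error is then about 20.4 × √(4 × .99 / 4000) = 0.64, and power at −2.5 is about 97%. The power loss therefore depends on the plan's own variance formula. The bias in γ11 does not.

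Stronger readings are tempting but not supported:
- That a successful intervention would probably be declared a failure: 79% or 51% power at −2.5 does not show this.
- That −5.0 is a pass/fail threshold: section 10.A makes it the strongest grade of support.
- That the sign could reverse through waning: section 1.B.2.2 reports a sustained benefit.
- That Table 4 declares two co-primary tests: it is a proposal for what to share with the DSMB, and its primary-analyses block includes descriptive summaries.

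**Conclusion.** The concern holds in this form. The coefficient tested in section 10.A is not the outcome defined in sections 2.A and 7.A. If a −5 mm Hg difference is reached early and sustained, the 24-month slope is −2.5 under the layout matching the power calculation, and about 0 to −4 across the other schedules tried. No single value in that range comes from the documents. It depends on visit timing, on the enrollment row and on readings extending into the second year; if nearly all fell in the first year, the 12-month rows of the table would be the better guide. At −2.5 the plan's implied standard errors give 79% or 51% power, against the 98% or more obtained by treating 5 mm Hg as an annual slope.

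The 12-month window reduces the problem without removing it, because the slope still moves with visit timing and can fall short of or overshoot −5. The results assume equal SBP at enrollment and a plateau from month 3, although the −2.5 figure needs only that the −5 is present at year 2.

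**What to change.** Reconcile section 10.A with section 15 (4.1, 4.5 and Table 4), and name one confirmatory H1.1 contrast: the between-arm difference in SBP at 12 months. Estimate it from all readings, using categorical time windows or a piecewise curve with an early knot, and test it at two-sided .05. State that enrollment SBP enters as a covariate. It should not be constrained equal across arms, because section 10.A.2 warns that enrollment may differ by arm once providers know the assignment. Make the 24-month trend secondary. Report the estimate and 95% CI against the 5 mm Hg benchmark, and restate the power for this contrast.

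The cost is SAP wording and model code, with no new patients or data. The downside is that a 12-month contrast from irregular routine readings may be somewhat less precise than a slope, and patients with no reading near 12 months contribute only through the model.

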### 10.A.2. Per Protocol Analysis Plan

Given the pragmatic, unblinded, cluster-randomized study design, there is potential in this study for otherwise-eligible patients to not be enrolled, and for enrolled patients to subsequently seek treatment interventions (including no treatment) outside of their assigned protocol. Furthermore, we would like to know what the impact of actual receipt of the intervention (as opposed to clinic-level assignment) has on study outcomes. Therefore it will be desirable to conduct a per-protocol analysis (average effect of telehealth vs. best practice, had everyone followed the trial protocol) to complement the intention to treat (ITT) results of the primary analysis. Preliminary data suggests that the ITT approach in this study may be subject to bias due to 1) differential likelihood of enrollment based on provider knowledge of treatment assignment, and/or 2) differential self-selection of patients following through with the assigned treatment intervention. Because these processes operate post-randomization, the randomization scheme cannot ensure confounder balance by enrollment or treatment status, and the study population can be considered as analogous to an observational cohort.

Directed acyclic graphs (DAGs) have been used to depict causal relationships and illustrate potential sources of bias in epidemiologic studies. Briefly, DAGs consist of nodes (e.g., treatment, outcome, other variables) presented in temporal sequence and connected by arrows, which indicate potential causal pathways. If there is no arrow connecting two nodes, it can be assumed that no causal relationship exists. Where 'backdoor' paths can be identified, estimation of causal effects may be biased For this study a DAG might be drawn as depicted in Figure 1, where:

- **Z** is randomized treatment assignment;
- **S=1** represents selection (enrollment) into the study;
- **A** is actual treatment receipt (patient adherence to assigned intervention);
- **Y** represents BP-related study outcomes;
- **L** is a vector of observed patient prognostic factors (e.g., age, comorbidities);
- **U** represents a vector of (possibly unmeasured) patient characteristics predictive of adherence to the assigned intervention protocol.

